While these first findings of a protective effect of antidepressants in prodromal individuals add to an intriguing line of primarily indirect evidence suggesting that antidepressants, which have a favorable risk-benefit ratio, may influence the development of psychosis, the lack of randomization and potential of prescriber bias reduce the interpretability of these early data. Therefore, we now propose to conduct a randomized, controlled 6-month pilot study comparing the antidepressant fluoxetine with the second generation antipsychotic aripiprazole in 48 subjects aged 12-25 years with at least moderate attenuated positive symptoms that developed within the past five years. Since transition to psychosis can occur at a relatively low rate over a very variable and potentially long time frame, and since discontinuation rates in long-term studies of putatively prodromal cohorts have been very high, we have designed a randomized, double-blind study focusing on intermediate outcomes, including the composite of all-cause-discontinuation and/or addition of a major psychotropic medication (see below), symptom change, safety, and adherence. The specific aims are:

Specific Primary Aim 1: To compare fluoxetine and aripiprazole on the likelihood of and time to all-cause discontinuation/need to add another psychiatric medication, symptomatic improvement, and adverse effects

Primary Hypothesis 1: Compared to aripiprazole, significantly fewer patients on fluoxetine will either discontinue treatment or require the addition of an antipsychotic, mood stabilizer, antidepressant or of >3 weeks of treatment with an anxiolytic/hypnotic

Secondary Hypothesis 1: Compared to aripiprazole, time to all-cause discontinuation or need to add another psychiatric medication (as defined above) will be significantly longer with fluoxetine

Secondary Hypothesis 2: Compared to aripiprazole, changes in attenuated positive, negative and general psychopathology will be similar with fluoxetine.

Secondary Hypothesis 3: Compared to aripiprazole, fluoxetine will be associated with significantly lower rates of adverse effects.

Specific Secondary Aim 1: To compare the effect of fluoxetine and aripiprazole on social and role functioning and subjective well-being in individuals at risk for schizophrenia.

Primary Hypothesis 1: Compared to aripiprazole, fluoxetine will lead to significantly greater improvement in social and role functioning.

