the predetermined time points independent of whether they are compliant with the study protocol to allow for an ITT analysis. The primary outcome variable for this project will be discontinuation of medication or addition, as verified by prescription, of another psychotropic medication to the daily treatment regimen of the subject (excluding prn medications). Patients that are not compliant at least 80% of the time will be subject to an unscheduled study termination.

Optional Genetic Test Component

Once during the study period, each subject will be asked to provide an additional 16 ml blood sample (approximately 1 tablespoon) for DNA collection and genotyping. The collected blood samples will be stored in locked freezers. Blood samples will be transferred to the Feinstein Institute for Medical Research ([name] lab) Human Genetics Program core facility for lymphocyte extraction. From this lymphocyte extraction, 50% will be used for direct DNA extraction and 50% will be utilized to establish Epstein-Barr virus-transformed cell lines. We will store the DNA for future exploratory analyses comparing patients with conversion to psychosis or worsening of prepsychotic symptomatology to those patients who did not worsen or convert. These exploratory analyses will target potentially relevant genomic regions involved in schizophrenia and genomic regions involved in conversion to psychosis potentially identified by then in other prodromal research cohorts.

Analytic Plan

General Considerations. All analyses will be conducted in an ITT sample using all randomized patients who received at least one dose of medication. Although the analytic methods to be described below (i.e. survival analysis, mixed models, RMANOVA, etc.) are fairly routine, missing data can cause problems in the statistical analyses. Thus, if the necessary, we will consider the use of multiple imputation techniques (i.e., PROC MI and PROC MIANALYZE), using the assumption of data being "missing at random" (MAR). In this case, we will transform non-monotone missing data patterns to monotone patterns, which are easier to analyze.

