Specific Primary Aim 1. *To compare fluoxetine and aripiprazole on time to all-cause-discontinuation/need to add another psychotropic agent, prodromal symptom change and adverse effects in prodromal individuals.* Binary outcomes, such as the primary composite outcome variable and the dichotomized presence of specific side effects (i.e., present=moderate severity or higher) or non-adherence, will be analyzed using chi squared test or Fischer's Exact test, as necessary. Standard methods of survival analysis (Kaplan-Meier product-limit method, logrank test, Cox proportional hazards regression) will be applied to the secondary, time dependent variable "time until all-cause-discontinuation/need to add another psychotropic". If during the trial a subject is lost to follow up, that subject's data will be "censored" at the week of dropout. Cox proportional hazards regression model will be used to determine which factors (if any) are predictive of all cause discontinuation. In addition to the ITT analyses, we will also conduct a sensitivity analysis using only data from subjects as long as they remained on the assigned treatment, censoring data at the week of treatment discontinuation.

Repeated measures analysis of variance (RMANOVA) using a mixed models approach (SAS PROC MIXED, SAS Institute, Cary, NC) will be used to examine the longitudinal and between-drug patterns in continuous outcomes, such as psychopathology rating scores and severity of side effects. In case of relevant missing data, PROC MIXED will be able to model the data despite the missing values. RMANOVA using the mixed models approach will be utilized to analyze changes in weight, BMI and HOMA-IR (using the log ratio transformation). The method of generalized estimating equations (GEE) will be used to analyze ordinal data, such as Barnes and Simpson-Angus scores.

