Exploratory Aim. To compare the effect of fluoxetine and aripiprazole on BDNF levels to determine potentially beneficial neurotrophic effects that mediate symptomatic and/or functional benefits. Similar statistical methods as for the continuous outcomes in aim 1 and aim2 will be used.

Power Calculations and Sample Size. This is a pilot study with the aim to assess the feasibility of this design for a larger trial and to obtain preliminary data that would guide future power and effect size analyses. For the purposes of this trial, we used an estimate of a 40% difference between the two treatments on the combined primary outcome of all-cause-discontinuation and need for addition of another major psychiatric medication. Based on preliminary data, we estimated the rates to be 65% with antipsychotics and 25% with antidepressants. With 24 subjects in each treatment arm, we will have 82% power to find a statistical difference in the primary composite outcome in a two tailed t-tests with alpha <.05 (online calculator used for this power/sample size calculation: <http://www.stat.ubc.ca/~rollin/stats/ssize/b2.html>). This is a conservative estimate, as repeated

measures ANOVA will yield greater power, compensating for any drop outs prior to the first post-baseline assessment.

HUMAN SUBJECTS

This human subjects research meets the definition for clinical research.

Protection of Human Subjects

1. Risks to the Subjects

Fluoxetine is approved by the Food and Drug Administration (FDA) for the treatment of depression, obsessive-compulsive disorder (OCD), and panic disorder in adults and for depression, anxiety and OCD in children and adolescents. Aripiprazole is approved by the FDA for the treatment of schizophrenia and bipolar disorder in adults and in children and adolescents age 10-17 (bipolar disorder) and age 13-17 (schizophrenia). Neither medication is specifically indicated in adolescents for the symptoms for which they are prescribed in this trial. However, both medications are widely used for a range of disorders in children and adolescents, and both have been used successfully in the RAP Program. This study includes detailed procedures for safety monitoring.

These procedures are outlined below.

There are a number of common, non-serious side effects associated with use of [fluoxetine](#): nausea, diarrhea, intestinal discomfort, headache, insomnia, sexual side effects, dry mouth, fatigue/drowsiness and dizziness.

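### Ratings made after stopping or adding a drug can hide part of an aripiprazole advantage behind a finding of similar symptom change, and the on-treatment analysis does not clearly remove them

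*Combined protocol and SAP*

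**What the plan says.** Under Specific Aims, Secondary Hypothesis 2 reads: "Compared to aripiprazole, changes in attenuated positive, negative and general psychopathology will be similar with fluoxetine". No margin or equivalence test goes with it.

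The Analytic Plan (General Considerations) says: "All analyses will be conducted in an ITT sample using all randomized patients who received at least one dose of medication". The Assessments text says that patients who stop the assigned drug, or start one the protocol does not allow, have a termination visit but are still rated at "the predetermined time points independent of whether they are compliant with the study protocol to allow for an ITT analysis". Table 2 schedules SIPS/SOPS and BPRS at every visit to Week 24.

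Under Specific Primary Aim 1, in the paragraph on binary and survival outcomes, the plan adds: "we will also conduct a sensitivity analysis using only data from subjects as long as they remained on the assigned treatment". Its stated cut-off is the week of treatment discontinuation. The next paragraph introduces the mixed models for symptom scores and does not mention this analysis.

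For the composite of discontinuation or added medication, Power Calculations and Sample Size says: "we estimated the rates to be 65% with antipsychotics and 25% with antidepressants".

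**The concern.** Keeping all ratings regardless of treatment is usually cautious when the aim is to show a difference. It need not be cautious when the aim is to show similarity, because ratings made off the drug, or on another drug, may no longer reflect the drug assigned. Here the events are expected to be frequent and unequal. The composite counts an added antipsychotic or antidepressant, so patients in one arm may be rated while taking the other arm's drug class.

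The case for fluoxetine would combine better retention with similar symptom change. If aripiprazole is in fact better on symptoms while taken, the retention difference could itself help to make symptom change look similar. The on-treatment analysis is the natural safeguard, but as worded it may not reach symptom scores, and it may keep ratings made after a second drug was added.

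**Working it through.** **Reproducing the plan's figure.** Inputs from Power Calculations and Sample Size: 65% and 25%, 24 per arm, two-sided 0.05. With the pooled-variance normal approximation, the pooled rate is 0.45, the null SE is √(2×0.45×0.55/24) = 0.1436 and the alternative SE is √((0.65×0.35 + 0.25×0.75)/24) = 0.1315. Then (0.40 − 1.96×0.1436)/0.1315 = 0.90, which gives 81.6% power against the stated 82%. The rates can be used as the plan's own.

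**Who is still on the assigned drug alone.** By Week 24, 0.65×24 = 15.6 aripiprazole and 0.25×24 = 6 fluoxetine patients have had an event. That leaves 8.4 (35%) and 18 (75%).

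**Week 24 formula.** Let a and f be the on-drug improvements on aripiprazole and fluoxetine in SD units, and m a common improvement after the event. The documents give no values for these, so all are assumptions, and every event patient is taken to be still rated.

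ITT difference = (0.35a + 0.65m) − (0.75f + 0.25m) = 0.35a − 0.75f + 0.40m

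| a | f | m | Aripiprazole mean | Fluoxetine mean | ITT difference | On-drug difference |
|---|---|---|---|---|---|---|
| 0.8 | 0.4 | 0 | 0.28 | 0.30 | −0.02 | 0.40 |
| 0.8 | 0.4 | 0.3 | 0.475 | 0.375 | 0.10 | 0.40 |
| 0.8 | 0.4 | 0.6 | 0.67 | 0.45 | 0.22 | 0.40 |
| 0.8 | 0.8 | 0 | 0.28 | 0.60 | −0.32 | 0 |
| 0.8 | 0.8 | 0.3 | 0.475 | 0.675 | −0.20 | 0 |
| 0.8 | 0.8 | 0.6 | 0.67 | 0.75 | −0.08 | 0 |

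The first three rows are one illustrative Week 24 scenario: an aripiprazole advantage shrinks or vanishes. In the last three the drugs are equal, and a gap appears in fluoxetine's favour.

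**A general bound.** The ITT difference minus the on-drug difference is −0.65a + 0.25f + 0.40m. If a > f and m ≤ a, this is at most −0.25(a − f), so at least a quarter of the advantage is lost at Week 24.

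**Other post-event patterns**, as the share of (a − f) that survives at Week 24:
- event patients take on the other drug's effect: (0.35 − 0.25)a − (0.75 − 0.65)f, so 10%
- all take on a fluoxetine-like effect: 35%
- all take on an aripiprazole-like effect: 75%
- each arm keeps its own benefit: 100%

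**Averaged over visits.** The plan does not say which contrast of the mixed model decides the question. Under an assumed constant hazard, the average share of the ten post-baseline visits (Weeks 1, 2, 3, 4, 6, 8, 12, 16, 20, 24) that fall after the event is 30.8% and 10.5%. The difference becomes 0.692a − 0.895f + 0.203m. With a = 0.8, f = 0.4 and m = 0, 0.3, 0.6 it is 0.20, 0.26 and 0.32 SD, so about 51%, 36% and 21% of the 0.40 SD is hidden. The bound weakens to 0.105(a − f), about a tenth.

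**The case against.** A reader might infer that 65% against 25% must pull the arms together, so that similarity follows by construction. The documents do not support that. With equal efficacy, which is what the hypothesis expects and is closest to the similar positive-symptom improvement reported under Preliminary Data, the same formula moves the arms apart unless the benefit persists. A reader might also take the Week 24 illustration to mean that 45% to 100% of a true difference is hidden. That range belongs to one assumed pair of effects and the least favourable time point.

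Other points stand in part:
- An on-treatment analysis is planned, under an aim that covers symptom change, so the conclusion need not rest on ITT data alone. What stands against the plan is that its scope and cut-off are unclear. The termination visit after a disallowed drug could be read as ending assigned treatment, but the text does not say so. Lorazepam is an allowed adjunct, yet more than three weeks of an anxiolytic counts toward the composite.
- Not every event means loss of the drug, and patients lost to follow-up supply no later ratings. The 35% and 75% are therefore not the exact mix of data.
- ITT answers a legitimate question about the policy of starting each drug. The plan does not say that this is what similar refers to.
- This is a 48-patient pilot and the hypothesis is secondary. At 24 per arm the 95% interval half-width is about 1.96×√(2/24) = 0.57 SD at a single time point, so imprecision and the missing margin weaken a similarity claim in any case.

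**Conclusion.** The point holds as a risk with no fixed direction. The main symptom comparison includes post-event ratings, and the planned event rates are high and unequal. If aripiprazole is better while taken and post-event benefit is common to both arms and no larger than aripiprazole's, at least a quarter of the advantage is hidden at Week 24, or about a tenth averaged over visits under a constant hazard. The loss can be larger, and it is nil if each arm keeps its own benefit. With equal efficacy and benefit lost, the error is instead an apparent fluoxetine advantage.

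The effect sizes are assumptions; the event rates are the plan's. The gap in the documents is that the on-treatment analysis is not tied to symptom scores and is cut only at discontinuation. Ratings on fluoxetine plus an added antipsychotic could therefore sit in both analyses. This should be fixed before any statement that symptom change is similar.

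**What to change.** In the SAP, for Secondary Hypothesis 2:

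- State that the on-treatment analysis applies to the mixed-model symptom outcomes, and cut each patient's data at the first of discontinuation or addition of another psychotropic as the composite defines it. Specific Aims and Assessments word that addition differently, so name one definition.
- Report the on-treatment estimate and 95% interval beside the ITT result, with the number still on the assigned drug alone by visit and arm.
- Do not conclude that symptom change is similar if the two analyses disagree; report both.
- Set a criterion (margin) for similar. This is a separate gap, but the rule above cannot operate without it.

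The cost is SAP wording and one changed cut-off; no new data are needed. There are two downsides. The similarity claim becomes harder to make: with about 8.4 and 18 patients left at Week 24, the single-time-point half-width is about 1.96×√(1/8.4 + 1/18) = 0.82 SD, although a mixed model that uses earlier visits may do better. And patients who stay on drug are selected after randomisation, so the on-treatment analysis supplements ITT and does not replace it.

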Adjunctive Therapies. Based on our previous experience with administration of fluoxetine and aripiprazole in prodromal patients, we expect the need for rescue medication to be relatively infrequent. However, adjunctive medication will be available to address clinically relevant, treatment emergent side effects. These include: benztrapine (up to 2 mg bid) for extrapyramidal symptoms (EPS) in case dose reduction is ineffective or undesired; lorazepam (up to 1 mg bid) to treat restlessness, anxiety or agitation, or to improve sleep; and propranolol (up to 20 mg tid) for akathisia. Moreover, when a patient develops $\geq 7\%$ weight gain, which triggers healthy lifestyle interventions involving simple education regarding diet and physical activity, and despite this exceeds 10% weight gain, metformin (500-2000 mg) will be offered. After the patient is symptom free for at least two weeks a slow withdrawal of the adjunctive medication will be attempted. Patients will also receive supportive psychotherapy by during regular medication visits. Needs based individual psychotherapy will be provided for crisis situations and in a time limited fashion (i.e., six sessions).

Assessments. Table 2 summarizes the proposed diagnostic, efficacy and safety assessments throughout the 24-week study. Subjects can still be assessed ± 7 days of their proposed assessment date in the event that there are unable to come in at the proposed time.

The ACISR Trials Operation Unit maintains a cadre of trained raters and assessors with experience in the majority of measures utilized, the Clinical Assessment Strategies Unit has been instrumental in the development of individual assessment measures of patient function, and the Adverse Event Unit provides expertise in the assessment and management of drug-induced adverse events, of particular importance in this population who may be more sensitive to drug side effects, and which may predict non-adherence.

Patients who discontinue the assigned medication or who initiate treatment with a medication that is not allowed as per the protocol will have an unscheduled study termination visit, but patients will be assessed at

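### The time-to-all-cause-discontinuation analysis censors patients lost to follow-up, although their loss is part of the endpoint, and the primary test has no rule for them

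*Combined protocol and SAP*

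**What the plan says.** Secondary Hypothesis 1 in the Specific Aims is that "time to all-cause discontinuation or need to add another psychiatric medication (as defined above) will be significantly longer with fluoxetine". In the Analytic Plan, Specific Primary Aim 1, the survival methods "will be applied to the secondary, time dependent variable 'time until all-cause-discontinuation/need to add another psychotropic". The next sentence sets the rule for loss to follow-up: "If during the trial a subject is lost to follow up, that subject's data will be 'censored' at the week of dropout".

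The Assessments section limits how many patients this affects. Those who stop the assigned drug or start a disallowed one have an extra visit at that point. Their follow-up is not cut short; the plan keeps to "the predetermined time points independent of whether they are compliant with the study protocol to allow for an ITT analysis". A discontinuation or add-on recorded before a later loss therefore stays an event.

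The same section defines the primary outcome: "The primary outcome variable for this project will be discontinuation of medication or addition, as verified by prescription, of another psychotropic medication". Loss to follow-up is not mentioned. The primary test falls under "Binary outcomes, such as the primary composite outcome variable", to be compared by chi-squared or Fisher's exact test, again with no rule for lost patients.

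A sensitivity analysis is planned "using only data from subjects as long as they remained on the assigned treatment, censoring data at the week of treatment discontinuation". The plan does not say which outcomes it covers.

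**The concern.** The endpoint is labelled all-cause, so leaving treatment for any reason should count. A patient who disappears before week 24 with no recorded event has, as far as the trial can tell, stopped assigned treatment. Censoring treats that patient as someone who would have gone on with the same risk of discontinuing as those still under observation. That is not credible when dropout is itself a component of the outcome.

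The censored patient still contributes time at risk until dropout; what is lost is the event. The curves and hazard ratio for Secondary Hypothesis 1 would then describe recorded discontinuation or add-on, which is a narrower endpoint than the one named. The Power Calculations section says this pilot should inform the planning of a larger trial, so understated event rates would be carried forward.

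Two gaps sit beside this. Without a rule for the primary binary test, the classification of lost patients could be chosen after the data are seen. And if the on-treatment sensitivity analysis is applied to the composite, it censors the discontinuation event itself.

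**Working it through.** **Inputs from the plan.** 24 patients per arm; composite rates of 65% (antipsychotic) and 25% (antidepressant); two-sided alpha 0.05; stated power 82% (Power Calculations and Sample Size); 24 weeks of follow-up (Study design).

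**Assumptions.** The plan gives no loss rate. Let s be the share of all composite events in an arm that are losses with no earlier recorded event. The 65% and 25% are taken to include such losses, and event times to be exponential.

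**The plan's own figure.** Pooled-variance normal approximation for two proportions, mean rate 0.45:

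- SE under the null = √(2 × 0.45 × 0.55 / 24) = 0.1436
- SE under the alternative = √((0.65 × 0.35 + 0.25 × 0.75) / 24) = 0.1315
- z = (0.40 − 1.96 × 0.1436) / 0.1315 = 0.90, so power is 81.6%, in agreement with 82%.

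**Hazard ratio and Kaplan-Meier rates.** Cumulative hazards to week 24 are H = −ln(0.35) = 1.050 for aripiprazole and −ln(0.75) = 0.288 for fluoxetine; their ratio is 3.65. Censoring a share s of events multiplies each H by (1 − s), and the Kaplan-Meier rate becomes 1 − exp(−H(1 − s)). For example, shares of 30% and 15% give a ratio of 3.65 × 0.70 / 0.85 = 3.01.

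**Logrank power.** 60,000 simulated trials per scenario, times rounded up to whole weeks, the stated share of events recoded at random as censored at the event week, rejection at |z| > 1.96. Expected events are 24 × (0.65 + 0.25) = 21.6 with none lost, and 17.3, 15.1 and 10.8 at equal shares of 20%, 30% and 50%.

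| Share lost, aripiprazole/fluoxetine | Hazard ratio | Week-24 rates | Logrank power |
|---|---|---|---|
| none | 3.65 | 65% vs 25% | 83% |
| 20%/20% | 3.65 | 57% vs 21% | 73% |
| 30%/30% | 3.65 | 52% vs 18% | 67% |
| 50%/50% | 3.65 | 41% vs 13% | 53% |
| 20%/10% | 3.24 | 57% vs 23% | 68% |
| 30%/15% | 3.01 | 52% vs 22% | 57% |
| 50%/25% | 2.43 | 41% vs 19% | 33% |
| 15%/30% | 4.43 | 59% vs 18% | not run |

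Schoenfeld's formula gives slightly higher power for the equal-share rows: 85% with none lost, then 77%, 71% and 57%.

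**Type I error.** With 45% in both arms, the nominal 5% test rejects 5% at 30%/30%, 5.8% at 20%/10%, 6.8% at 30%/15%, 11% at 50%/25% and 15% at 60%/30%. When losses are commoner on aripiprazole, the excess favours aripiprazole; at 15%/30% it is also 6.8%, in the other direction.

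**Primary binary test.** Exact enumeration over all 25 × 25 tables gives power of 84% (uncorrected chi-squared) and 75% (Fisher) at 65% vs 25%. If a 30% share in each arm is coded as non-events, the rates are 0.65 × 0.70 = 45.5% and 0.25 × 0.70 = 17.5%, and power is 57% and 45%. By the normal approximation (81.6% with losses as events), excluding the same patients gives 72%. Coding only fluoxetine losses, 0%/30%, as non-events gives 65% vs 17.5% and 94%. The unstated choice can move the result either way.

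**The case against.** The documents never say that loss to follow-up is a discontinuation. The outcome is defined by stopping the drug or by a verified prescription, and drug status at the time of loss is unknown. That is fair: counting losses as events is inferred from the all-cause label. But the label and the censoring rule then conflict in adjacent sentences, and the missing definition is part of the defect.

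Other text might be thought to cover the gap. General Considerations fixes the denominator (randomised and dosed at least once) and mentions multiple imputation under missing at random. The Assessments section terminates patients below 80% compliance, and Protection against risk lists exit rules. These may turn some losses into recorded terminations first and so shrink the share affected, although the plan does not say whether such terminations are events. None of them sets the event status of a lost patient: a denominator is not an event rule, and imputation is only to be considered and is not tied to this composite.

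The figures rest on assumed shares and on 65% and 25% including losses. If those rates are for recorded events only, the power losses shown do not apply. The mismatch with the all-cause label would remain, as would the bias under unequal shares. The 50-60% shares are the upper end of the range, and at moderate shares the type I error inflation is small. The explicit rule affects a secondary endpoint in a 48-patient pilot. All of this limits the size of the problem without removing it.

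**Conclusion.** The censoring rule is wrong as written for the endpoint it serves and should be corrected before analysis. Its reach is limited to patients lost with no earlier recorded event.

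With equal shares of loss in the two arms, the hazard ratio is unbiased, but event rates are understated and power falls by about 10 points at a 20% share and 16 at 30%. With unequal shares the hazard ratio is biased in either direction and the type I error exceeds 5%. Equal shares cannot be taken for granted: the Specific Aims describe very high discontinuation in such cohorts, and Preliminary Data report adherence of 61% on antidepressants against 21% on antipsychotics. That is adherence and not loss, but it points to a difference between the arms.

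For the primary test the fault is an unstated rule. The point about the on-treatment analysis is conditional on its being applied to the composite.

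**What to change.** - Count loss to follow-up before week 24 as an all-cause discontinuation event, dated at the last week the patient was known to be on study drug.
- Censor only event-free patients, at week 24 or at an administrative closure of the study or site.
- State the same rule for the binary primary composite.
- Keep the analysis that censors losses as a sensitivity analysis.
- State that the on-treatment analysis is limited to symptom, function and side-effect outcomes.
- Report composite events by component and by reason, with losses to follow-up shown separately by arm.

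The cost is a few sentences in the Analytic Plan. No new data or patients are needed.
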